5.6. Developmental Safety Update Report

A developmental safety update report will be submitted to the appropriate Competent Authorities and Research Ethics Committee, once a year for the duration of the trial. The time frame for the report starts with the date of first authorisation by a competent authority in an EU member state and the report should be submitted within 60 days of the anniversary of first authorisation.

5.7. Pregnancies

Pregnancy is an exclusion criterion for enrolment and patients of child-bearing age (premenopausal female capable of becoming pregnant) will take a pregnancy test if randomised to the levetiracetam arm.

All female patients of child-bearing age will be advised to use contraception throughout the trial. There are no known contraceptive drugs which are contraindicated while taking levetiracetam.

Acceptable methods of contraception include:

- Combined (estrogen and progestogen containing) hormonal contraception associated with inhibition of ovulation
 - oral
 - intravaginal
 - transdermal
- Progestogen-only hormonal contraception associated with inhibition of ovulation
 - oral
 - injectable
 - implantable
- Intrauterine device (IUD)
- Intrauterine hormone-releasing system (IUS)
- Bilateral tubal occlusion
- Vasectomised partner
- Barrier method Condom, with or without spermicide
- Barrier method Cap, must be used with spermicide

Any female patients of child bearing age randomised to the levetiracetam arm will be asked to contact their local site immediately, should there be any possibility they have become pregnant. The local site will arrange for a face-to-face visit as soon as possible and for the patient to have a urine pregnancy test and if positive, the study drug will be stopped and reasons given. Should the patient have had seizures, the decision whether or not to alter drug dose for seizure management will be the decision of the treating doctor.

During the follow up visits, whether face-to-face or telephone/video-call, any female patients of child bearing age randomised to the levetiracetam will be asked to confirm if there is any chance they have become pregnant since their previous visit. If there is any possibility the site will arrange for a urine pregnancy test. If the follow up visit is to be by telephone / video interview, the patient will be asked to attend their site. As above, if the test is positive, the study

drug will be stopped if the patient has been seizure free and reasons given. If seizures have occurred, the seizure management will be the decision of the treating doctor.

Any female patient who reports a pregnancy while on the trial will be followed up to determine outcome, including spontaneous or voluntary abortion, details of birth and presence or absence of any birth defects, congenital abnormalities or maternal or newborn complications. Any birth defects or congenital abnormalities must be reported as SAEs.

Pregnancy should be reported to PHS within 24 hours of becoming aware by completing the pregnancy case report form on the electronic data capture system. An email should be sent to [contact] to notify PHS that a pregnancy has occurred.

6. DATA MANAGEMENT

All data will be handled, computerised and stored in accordance with the Data Protection legislation and Public Health Scotland Confidentiality Guidelines.

6.1. Data Collection

Data generated will be entered by site staff onto a Trial specific eCRF. SCTRU will be responsible for checking the data, and validating it. All source data should be recorded within patient files.

The data collected will include:

- initial clinical details at randomisation
- drug administration (CTIMPs)
- adverse events
- survival/ recurrence details
- patient questionnaires

During the SPRING trial the Covid-19 pandemic has led to lockdown and patient shielding. As such, data regarding suspected Covid-19 illness dates and Covid-19 test results will be gathered.

6.2. Record Keeping and Archiving

PHS will store study documentation until the end of patient follow up. The documentation will then be archived according to current legislative requirements.

6.3 Data Security

The Trial eCRF system will be hosted by Elsevier Macro with full systems administration to allow user role management. Remote access requires a 128-bit encrypted password rdp connection. The system has a full audit trail and system log to track user activities. Elsevier security measures include managed gateway firewalls, anti-virus protection, and data back up

using dedicated data protection software. The Elsevier data centre is ISO 27001 Information Security Management certified.

In the event of a data security breach, SCTRU will follow the Public Health Scotland (PHS) Information Governance, Information security, and Adverse event management policies.

Patient and Carer questionnaires will be accessed via REDCap if patients or carers elect to use this option. REDCap is a data neutral secure web application for building and managing online surveys and databases and is compliant with 21 CFR Part 11, FISMA, HIPAA, and GDPR.

7. STATISTICS

7.1. Sample Size

Estimate of 1 year seizure rate in patients with suspected cerebral glioma after surgery is 20%. We anticipate a reduction in seizure rate to 10% in the treatment arm. Based on a 90% power to identify an improvement in 1 year seizure rate in the treatment arm compared to the control arm, this requires 532 patients across the two arms with a two-sided type I error level of 5%. Assuming a 24.8% 1 year mortality rate and that 12% of patients will be lost to follow-up, the final (maximum) sample size is 402 per arm.

Patients will be randomly assigned at a 1:1 ratio to the following groups:

• **Group 1**: Levetiracetam 500mg twice daily for 2 weeks, then increasing to 750mg twice daily thereafter for 1 year. Patients should have a minimum of 2 doses of 500mg prior to surgery. In those with moderate chronic kidney disease (eGFR 30-59 mL/min/1.73

m2) a starting dose of one 250mg twice a day for 2 weeks, then increasing to 500mg twice a day thereafter).

• **Group 2**: no AED treatment (standard care)

We anticipate an initial 6 month start up period, recruitment over 3 years, 1 year follow-up period and a further 9 months for data cleaning, analysis and report writing (total 65 months).

Conservative estimate of 1 year seizure rate in patients with suspected cerebral glioma after surgery is 20%. Based on the effect of levetiracetam of reducing seizure in patients with epilepsy we anticipate a reduction in seizure frequency to 10% in group 1.

Attrition due to limited Life Expectancy

The proportion of expected participants have been taken from the recognised potential frequency of cerebral glioma (low grade (Grade 1-2)/ high grade (Grade 3-4)¹¹⁻¹⁴. There will be a smaller proportion of high-grade cerebral glioma, as a higher proportion of grade 4 (Glioblastoma Multiforme) have a poorer performance status, which may preclude entry into

the study. However, more cases with grade 1 and grade 2 tumours will present with seizures, therefore will not be suitable for this study. On balance, we think that the proportion of cases with each grade are justifiable and are likely to represent the proportion recruited who would be at risk of first seizure.

The median survival statistics and mortality by 1 year for each grade of cerebral glioma (Grade 2-4) have been taken from routine "standard of care" randomised control trial papers for treatment: Grade 4¹¹⁻¹⁴. There are no suitable trials in grade 1 cerebral glioma, but we anticipate there will be relatively few of these and therefore have included the percentage number of cases in with the frequency of grade 2 tumours (Table 5).

Table 5:

| Tumour Type | Proportion of study population | Median Survival(months) | Mortality by 1 year | Mortality as a % of population | Attrition due to mortality |
|------------------|--------------------------------------|----------------------------|------------------------|--------------------------------------|----------------------------------|
| Grade 4 (GBM) | 65% | 14.6 | 38.4% | 25.0% | 22.2% |
| Grade 3 | 20% | 39/57 | 10.0% | 2.0% | 1.8% |
| Grade 2 | 15% | 84 | 6.8% | 1.0% | 0.9% |
| Total | 100% | | | 28.0% | 24.8% |

We have estimated an attrition rate in this population of 24.8% due to mortality at 1 year

Attrition Rate drop-out due to Adverse Events

In general in epilepsy studies, treatment failure for unacceptable side-effects is largely limited

to the early post-randomisation period. We wish to gain the earliest effect, because of the risk of early seizures (up to 5% in first post-operative week) in cerebral glioma patients, but appreciate that early attrition could be a problem if there was drop out due to intolerable side effects. It is recognised that levetiracetam has fewer early adverse events due to rash or haematological toxicity and drug-drug interactions than first generation AEDs (phenytoin, carbamazepine) and lamotrigine.

In a systematic review of the literature around levetiracetam dose and drop outs from study - we have looked at:

- a) Dropout rates in RCT of levetiracetam vs. Carbamazepine for non-tumoural resistant epilepsy. (Staring dose 500mg bid and increased as necessary to 1.5gr bid). Withdrawal rates were 14.4% with levetiracetam and 19.2% with carbamazepine⁵.
- b) Dropout rate in RCT of intravenous levetiracetam vs. Phenytoin for prophylactic seizures after craniotomy) (levetiracetam 11% vs. Phenytoin 13% at 3months)⁶.
- c) Dropout rate in RCT of levetiracetam vs. Phenytoin post-operatively in cerebral glioma patients who had previously had a seizure pre-operatively. (Starting dose oral 1 gram bid and altered accordingly). Levetiracetam had fewer side effects at 3 and 6 months and there were no drop-outs because of side effects at 6 months. 73% of patients taking

levetiracetam remained on the initial dose of 1,000 mg bid. (21% reduced their dosage to 500 mg bid, and 6% increased to a higher dose 1,500 mg bid because of seizure)²⁵.

The maximum dosage of levetiracetam used in SPRING will be 750mg bid. This is the World Health Organisation defined daily dose and is only 50% of the maximum recommended dose for resistant epilepsy.

We have estimated a dropout rate in this population of 12% due to intolerable side effects.

In the literature, a conservative estimate of frequency of seizures in the first year following surgery in cerebral glioma is >20%. Anti-epileptic drugs are effective at controlling tumour-associated epilepsy in 50% and reduce severity in 20-30%. Levetiracetam has a good side effect profile, but we have estimated a discontinuation rate of 12%. Cerebral cerebral gliomas are life limiting and we have estimated the attrition due to death from the disease at 24.8%.

Sample size was calculated to provide a 90% power to identify an improvement in 1 year seizure rate in the treatment arm compared to the control arm with a two-sided type I error level of 5%. This results in a requirement of 80 seizures (events) during the trial. Assuming a 24.8% 1 year mortality rate and that 12% of patients will be lost to follow-up the final (maximum) sample size is 804 (402 in each arm).

This is a two-arm phase III trial (90% power (1- β), 5% (α) 2-sided significance level) with a randomisation ratio of 1:1 (1: ϕ).

We use the odds ratio of the treatment arm and control as the primary outcome measure. The odds ratio is defined as the ratio of the odds of seizure in the treated group divided by the odds of seizure in the untreated group.

We assume the following 1 year seizure avoidance rates for the study arms

 $\lambda_0 = 0.80$ for control arm i.e. 20% seizure rate

 $\lambda_1 = 0.90$ for treatment arm (750mg BID) i.e.10% seizure rate

With a sample size of 532 this gives the following number of seizures in each study arm:

| | No AED | Levetiracetam |
|--------------------------|-----------|---------------|
| Seizure within 1 year | 53.2 (a) | 26.6 (b) |
| No seizure within 1 year | 212.8 (c) | 239.4 (d) |

The odds ratio can then be found as follows:

 $OR = (a \times d)/(b \times c) = 2.25$

From this we can see that the number of seizures required is a + b = 79.8 (rounded to 80).

If we experience a 1 year mortality of 24.8% and attrition through intolerable side-effects in 12% of patients then $N_{adjusted} = 532/((1-0.248)^*(1-0.12) = 803.9$ patients (rounded to 804). Therefore each arm should recruit 402 patients.

Recruitment Rate:

Estimates of number of patients that can be recruited from pilot sites, based on cases in each of the four centres over the last years, and a 50% recruitment rate, suggest that the study would be able to recruit over 989 patients over a 3 year period (see table 6 below).

| able 6: Recruitment Rate | | | | | | |
|--|--|----------------------------|--|--|--|--|
| | Estimate of patients recruited per month | Total for study (3 years)* | | | | |
| Liverpool | 4.25 | 153 | | | | |
| Edinburgh | 2 | 70 | | | | |
| Cambridge | 4.25 | 140 | | | | |
| King's college | 1 | 31 | | | | |
| Total for 4 sites | 11.5 | 394 | | | | |
| Average for 4 sites | 2.875 | 98.5 | | | | |
| Total for 11 additional sites (if similar to average | | | | | | |
| of 4 sites above) | 31.625 | 595 | | | | |
| Total for 15 sites | 43.125 | 989 | | | | |

[figure not shown]
Table 6: Recruitment Rate

(*These figures allow for a lag in opening site with sites opening in months 1,2,4,6,8,10,12,14,16,18,20,22,24,26 and 28.)

The figure below shows the recruitment figures projected for the full period of the study (36 months). This projection suggests that we could meet our recruitment target of 804 patients at month 32.

Figure 1: Projected number of patients recruited over the study period.

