3.4. Randomisation

After ensuring that the patients meet **all** eligibility criteria and has consented to participate in the study, sites will randomise the patient following the instructions described in the 'SPRING work instructions for sites.

Once a patient has been randomised, a patient study number will be issued and this should be used in all correspondence.

Informed Consent/Authorisation

All Patients that are eligible to receive therapy and randomised to AED arm must undergo an Electrocardiogram (ECG) and pregnancy test (if female and of child bearing age) prior to starting trial medication. AED arm patients must initiate treatment prior to surgery and have taken a minimum of two doses of 500mg Levetiracetam (two doses of 250mg in CKD3 patients) prior to surgery. See Patient Pathway (Page 7).

Prior to protocol enrolment and initiation of treatment, subjects must sign and date an approved consent form.

Eligibility Exceptions

Eligibility exceptions will not be granted.

Withdrawal of Subjects

Patients *discontinue* from the study drug for reasons such as safety or non-compliance. These patients will continue to be followed up for efficacy and safety as per protocol, unless they are lost to follow up or deceased. Patients may *withdraw* from the study at any point and they do not have to give a reason. However, we will ask the patient's permission to continue to collect information on their progress that is routinely recorded in their medical records. This is so that the overall quality of the study is not impaired. The patient can say no at this point and then no further data collection will take place, and will be censored at the point of withdrawal. This should be indicated on the case report form (CRF) as per completion guidelines.

Patients who consent to the trial but do not undergo planned surgery will be withdrawn from the trial. For any patient that did not undergo planned surgery, a further patient would be enrolled to the trial to maintain the target number of patients for analysis.

Please note that should it be medically required, participants in either study arm will be removed from the study and treated with appropriate medication according to standard care.

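### Section 7.1 reaches 804 patients and 90% power from a mortality figure and a 12% loss that the protocol itself contradicts; true power depends on assumptions it does not state

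*Protocol*

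**What the plan says.** All section references are to the protocol.

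- **Design inputs (7.1).** The control one-year seizure rate is 20%. For the other arm: "We anticipate a reduction in seizure rate to 10% in the treatment arm". The error rates are given as: "This is a two-arm phase III trial (90% power (1- β), 5% (α) 2-sided significance level". These lead to 532 evaluable patients.
- **Inflation (7.1).** The opening paragraph reads: "Assuming a 24.8% 1 year mortality rate and that 12% of patients will be lost to follow-up". The worked formula later in 7.1 describes the same two numbers differently: "If we experience a 1 year mortality of 24.8% and attrition through intolerable side-effects in 12% of patients". It divides 532 by (1 − 0.248)(1 − 0.12) to reach 804.
- **Mortality (7.1, Table 5).** The total row reads: "Total | 100% | | | 28.0% | 24.8". The 28.0% stands under mortality as a percentage of the population. The 24.8% stands under a different heading, attrition due to mortality. The step from one column to the other is not explained.
- **Origin of the 12% (7.1).** After reviewing drop-out in three levetiracetam trials, the protocol concludes: "We have estimated a dropout rate in this population of 12% due to intolerable side effects". A later paragraph calls the same 12% a levetiracetam discontinuation rate.
- **What happens to patients who stop the drug (3.4).** "These patients will continue to be followed up for efficacy and safety as per protocol", unless they die or are lost. Sections 7.3 and 7.3.1 make the primary analysis intention to treat.

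**The concern.** There are two conflicts. First, the text calls 24.8% the one-year mortality, while the table it comes from gives 28.0% for that quantity. Second, stopping levetiracetam is treated as leaving the analysis, and is taken from both arms although the control arm has no study drug to stop. Under section 3.4 and intention to treat, these patients stay in the comparison. They cost no sample size, but they may dilute the treatment effect. Meanwhile no allowance for genuine loss to follow-up is derived anywhere in 7.1.

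The stated power is what the funder, the data monitoring committee and readers of a null result will rely on. As written, it rests on a loss pattern that other sections of the protocol say will not occur.

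**Working it through.** **Formula.** Two proportions, pooled variance under the null, no continuity correction, with p̄ = (p1 + p2)/2 and d = p1 − p2:

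- n per arm = [1.960·√(2p̄(1−p̄)) + 1.2816·√(p1(1−p1) + p2(1−p2))]² / d²
- power = Φ{[d·√n − 1.960·√(2p̄(1−p̄))] / √(p1(1−p1) + p2(1−p2))}

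**Step 1: reproduce the plan.** With p1 = 0.20 and p2 = 0.10, n = (0.9897 + 0.6408)²/0.01 = 265.9, so 266 per arm and 532 in total. Then 532/(0.752 × 0.88) = 803.9, so 804. Both figures reproduce exactly.

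**Step 2: Table 5 mortality.** 0.65 × 38.4% + 0.20 × 10.0% + 0.15 × 6.8% = 24.96% + 2.00% + 1.02% = 27.98%, printed as 28.0%. The last column is about 0.89 of this: 24.8/28.0 = 0.886, with row ratios 22.2/25.0 = 0.888, 1.8/2.0 = 0.90 and 0.9/1.0 = 0.90.

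**Step 3: protocol formula with 28.0%, nothing else changed.** 532/(0.72 × 0.88) = 839.6, so 840. At 804, the evaluable number is 804 × 0.72 × 0.88 = 509.4 (254.7 per arm) and power is 88.7%.

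**Step 4: keep discontinuers in the analysis.** The evaluable number is then 804 × 0.72 = 578.9, or 804 × 0.752 = 604.6 if 24.8% is used. The levetiracetam arm rate depends on what 10% means. The protocol does not say, so each row is an assumption:

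- 10% on drug, discontinuers at 20%: 0.88 × 10% + 0.12 × 20% = 11.2%
- 10% on drug, discontinuers at 15% (half the benefit kept): 0.88 × 10% + 0.12 × 15% = 10.6%
- 10% already the arm-level intention-to-treat rate: 10.0%

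**Step 5: add true loss.** The last column applies a 10% loss in both arms. This is an assumption, taken from criterion D in section 7.3.3, where it is the highest loss at which the trial proceeds unamended. Evaluable: 804 × 0.72 × 0.90 = 521.0.

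| Levetiracetam arm rate | Power, 24.8% removed | Power, 28.0% removed | Power, 28.0% removed and 10% lost |
|---|---|---|---|
| 11.2% | 84.8% | 83.3% | 79.2% |
| 10.6% | 89.6% | 88.3% | 84.8% |
| 10.0% | 93.3% | 92.3% | 89.4% |

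**Step 6: deaths kept in the denominator.** With all 402 per arm analysed, and if 20% and 11.2% are rates among everyone randomised, power is 93.2%.

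**The case against.** The strongest reply is that the arithmetic is right and the plan may be conservative. Several parts of it stand.

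- **Meaning of the 10%.** The protocol speaks of the rate in the treatment arm, which allows an arm-level reading; power is then 92.3% at 28.0% mortality before any true loss. Elsewhere 7.1 ties the 10% to the target dose and to the drug's effect in epilepsy, and takes discontinuers out before reaching 532. That leans towards an on-drug rate but does not settle it.
- **Deaths.** Section 7.3.1 analyses seizure within one year by intention to treat and does not say deaths are excluded. Removing every death is cautious, because a patient who has a seizure and then dies has already reached the endpoint.
- **Control rate.** Section 7.1 calls 20% conservative. If the control rate were 24% and the halving held, full 12% dilution (13.44% in the levetiracetam arm) with 28.0% removed would still give 90.5%. At 25% (14.0%) it would be 91.8%. These control rates are illustrative.
- **Replacement.** Section 3.4 enrols a further patient for each one who has no surgery or is barred from the drug by the QT finding, so some attrition is covered elsewhere.

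Two stronger readings are tempting. A reader might infer that the trial is underpowered. The documents do not show this: the result falls on either side of 90% depending on points they leave open. A reader might also infer that 24.8% is mortality already reduced for drop-out, so that the 12% is counted twice. The ratio suggests it, but 28.0% × 0.88 = 24.6% and 25.0% × 0.88 = 22.0%, not the printed 24.8% and 22.2%. The column could instead mean deaths without a previous seizure. The protocol confirms neither.

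None of this removes the two contradictions in the text.

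**Conclusion.** The point holds as a fault in the inputs and labels of section 7.1, with a conditional effect on power. The mortality conflict alone is worth 36 patients (840 against 804), or 1.3 percentage points of power (90.0% to 88.7%). The treatment of the 12% matters more, and can move power either way. At 804 with 28.0% removed for death and discontinuers retained, power runs from about 83% to about 92%. A true 10% loss lowers those ends to about 79% and 89%. Keeping deaths in the denominator with an 11.2% arm rate gives about 93%.

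The lower figures assume that 10% is an on-drug rate and that discontinuers return fully to the control risk; the higher ones assume an arm-level 10% or that deaths are retained. The flat 90% follows exactly only if 24.8% die and 12% of both arms drop out of the analysis, which Table 5 and section 3.4 contradict. This should be fixed, but it does not invalidate the design.

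**What to change.** Keep 804 and rewrite section 7.1:

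1. Use 28.0% as one-year mortality, or explain what the 24.8% column represents and stop calling it mortality.
2. Give the 12% one label throughout, and treat it as possible dilution in the levetiracetam arm, not as loss from both arms.
3. State whether 10% is an on-drug or an intention-to-treat rate, and whether the planned rates count patients who die in the denominator.
4. Give a separate, justified allowance for true loss to follow-up.
5. Replace the flat 90% with the power, or range of power, that follows from these choices.

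The cost is a text revision and possibly a less favourable stated power. Recruitment, endpoint and primary analysis do not change, and no extra patients are needed.
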